Up to 100 patients will be consented in order to achieve at least 60 patients who will be randomly assigned and administered 0.5 mg/kg, 1mg/kg or placebo intravenous bolus after induction of anesthesia. A processed EEG device (SEDline, Masimo Corporation) will be used to gather raw EEG data for off line analysis among patients developing post-operative delirium. Patients will be screened for delirium with the CAM-ICU once per shift (3 times daily) for three days postoperatively. Currently, the CAM- ICU is performed by ICU nursing and documented in the electronic medical chart. Both CAM-ICU screens and SEDLine monitoring are part of the usual and customary practice associated with these cases at EUHM and it would be unusual for a case such as this to be performed without this clinical data. Pain will be assessed according to hospital protocol and postoperative opioid consumption will be determined from the medical charts.

Preoperative and postoperative cognitive assessment will be completed at the ENT clinic preoperative, and postoperative follow up visit (done by research assistant). Adverse

effects (e.g., hallucinations or nightmares) will also be evaluated for three days postoperatively.

Chart review, data collection/entry will be done by [name], research assistant and the research staff.

3. Background and Significance:

Delirium is a frequent post-operative complication of major surgery with a reported incidence of 10-70 % [1] [2] [3]. After major head and neck cancer surgeries the incidence of delirium is reported to be over 25% [3]. Delirium is associated with increased morbidity and mortality, prolonged length of hospital and intensive care unit (ICU) stay and functional and cognitive decline [4] [5] [6] [7]. A history of dementia or depression, chronic medical illness, male gender and age>60 years are consistently described as risk factors for delirium [8] [9]; in the head and neck cancer patient population length of surgery and alcohol consumption have been identified as well [3] [10]. Currently there is no effective prophylactic treatment for delirium identified. Even the treatment of delirium remains difficult [11]. A Cochrane review on delirium prevention in hospitalized patients came to the conclusion that there is a paucity of research in this area resulting from difficulties in delirium detection and confounding factors like pre-existing cognitive impairment or multiple medical problems [12].

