Recently a small randomized trial in cardiac surgery patients found a significant reduction in postoperative delirium (31% to 3%) when sub-anaesthetic doses of ketamine (0.5mg/kg) were given upon induction [13]. The same group further published data for improved postoperative cognitive function with ketamine in cardiac patients [13]. A follow up randomized prospective study in cardiothoracic patients looking at ketamine and delirium is currently recruiting (PODCAST).

Ketamine's benefits are thought to be based on its NMDA antagonism, HCN1 inhibitory effects and its anti-inflammatory properties [14]. Multiple studies have shown decreased post-operative pain with decreased post-operative opioid use when ketamine was administered during the surgery [15]. Interestingly a recent study showed that a single dose of ketamine had a prolonged two week lasting effect on patients with refractory depression [16].

Ketamine is a drug that has been in use for more than half a century, is inexpensive and has a wide margin of safety.

We are proposing a prospective randomized placebo controlled study to elucidate the effects of ketamine on postoperative delirium in the head and neck cancer population receiving “flaps”, administered peri-operatively.

4. Objectives:

Primary Aim:

Optimize our intraoperative treatment protocol for head and neck cancer patients to reduce the incidence of delirium and associated postoperative cognitive dysfunction. The hypothesis is that ketamine decreases delirium postoperatively in this high risk surgical patient population.

Secondary Aims:

1. Determine the dose response relationship for intraoperative ketamine and delirium reduction. Our hypothesis is that higher dose ketamine will lead to a more profound reduction in postoperative delirium.
2. Determine if a single dose of ketamine will reduce post-operative pain and opioid requirements. Our hypothesis is that the higher dose of ketamine will lead to a more profound decrease in objective pain scores.
3. Determine if raw EEG data can predict postoperative delirium during general anesthesia. Our hypothesis is that EEG patterns will correlate with incidence of post-operative delirium.
4. Evaluate length of ICU and length of hospital stay (done by medical chart review). Our hypothesis is that ketamine administration will not increase ICU/hospital stay.

5. Innovation, Impact & Leverage.

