The successful completion of this study will provide critical data on a therapeutic and/or prophylactic effect of perioperatively administered ketamine on postoperative delirium. Delirium has been associated with increased length of ICU and hospital stay, increased cognitive impairment/decline and mortality. Despite increasing evidence of ketamine's ability to reduce postoperative delirium in cardiac patients, its opioid sparing effects and decreased postoperative opioid needs, ketamine is not widely used. Clinicians are concerned that psychoactive properties (e.g., hallucination and dissociative states)

interfere with post-operative cognitive function. These side effects however are rarely seen when ketamine is used in subanaesthetic doses.

Additionally, EEG data will be used to determine if this tool can be a possible predictor of delirium.

Currently, the most common way to monitor brain function during surgery is via processed electroencephalogram (EEG) monitors (SEDLine). These devices use frontal or fronto-temporal EEG electrodes, to measure the electrical activity of the brain. A special computer program translates these brain waves into a dimensionless number that roughly correlates to the dose of anesthesia administered. A purpose of our research is to utilize the electrical information from the raw EEG signals to determine if EEG patterns can predict a propensity to develop postoperative delirium. Our approach is to probe deeper into the analysis of the EEG signal than simply depth of consciousness by developing a taxonomy of specific states leading up to and through emergence.

EEG technology measures the electrical potential generated by synaptic input onto the dendrites of cortical neurons. Although higher frequencies are attenuated somewhat by the skull, a wide range of frequencies can be observed even with the abbreviated montage typical for the commonly available devices. With a minimal amount of effort the EEG file is available for download from the device via USB stick. The sensors are pre-packaged with gentle adhesive and applied to the patient's forehead while the patient is awake and removed with a minimal amount of discomfort (similar to a Band-Aid).

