Although these EEG devices are not considered an ASA standard monitor for general anesthesia, many practitioners elect to place these sensors for routine cases as a monitor of depth of anesthesia. Several other benefits of these devices have been proven through the use of these devices and their utility as a standard monitor has been considered [17]. Previous experiments using abbreviated EEG records in this fashion have shown variations in the post-operative pain that correlated with their EEG patterns just before emergence from general anesthesia [18]. This is in contrast to the majority of the past studies using these devices that have focused on the predictive value of the number derived from the proprietary algorithm developed by the manufacturer. These algorithms reduce the EEG information into a single dimensionless number which roughly correlates with depth of anesthesia, although this concept has come under criticism. Our study involves quantitative EEG analysis of multiple electrodes placed over frontal brain regions of patients with co-morbid conditions. The value of EEG frequency

October 8, 2019

analysis in predicting delirium is unknown, but it has the potential to be an important tool in determining risk of delirium.

6. Approach:

Our aim is to optimize our perioperative treatment protocol for head and neck cancer patients in the operating room to positively impact ICU outcomes, by improving the incidence of delirium, associated postoperative cognitive dysfunction and pain control. This is a single center prospective randomized double blinded placebo controlled study that will be conducted at EUHM

Study arms:

1. 0.5mg/kg pre-incision bolus
2. 1.0mg/kg pre-incision bolus
3. Saline placebo pre-incision bolus

Standard general anesthesia will be applied with following standardized drugs:

Sevoflurane, fentanyl, hydromorphone, succinylcholine, rocuronium, cis-atracurium, lidocaine, propofol. Dosing and choice of above medications is at the discretion of the anesthesiologist.

Primary Outcome:

Delirium (measured by Confusion Assessment Method for Intensive Care Unit criteria, CAM-ICU) Measurements: Prior to surgery (baseline assessment upon study enrollment in ENT clinic) and postoperative days 0-3 (afternoon/evening on postoperative day 0, POD 1-3 measurements per shift as per Emory delirium protocol)

Secondary Outcomes:

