1. Pre- and postoperative cognitive dysfunction (assessed in ENT clinic at pre- and post-operative visits or at anesthesia preoperative clinic) with the Mini-Cog, Mini-Mental Status Examination (MMSE) and the Cognitive Failure Questionnaire (CFQ).
2. Pain assessment (Prior to surgery (baseline assessment upon study enrollment in ENT clinic) and postoperative days 0-3 (afternoon/evening on postoperative day 0, and POD 1-3 per Emory protocol every 4 hours). Assessed by observer-based Behavioral Pain Scale or Behavioral Pain Scale (Non-Intubated) with subsequent administration of patient-reported Visual Analog Scale.

October 8, 2019

3. Post-operative use of narcotics (assessed POD 0-3 from medical chart)
4. Off line EEG analysis to correlate with postoperative delirium

7. Participant Selection

Inclusion criteria:

Inclusion criteria:

1. Patients 18 years of age and older, with otolaryngeal cancer receiving surgery with general anesthesia.

(Please note we are purposefully including patients with higher predisposition to delirium as we are investigating potential preventive strategies for this diagnosis of multiple etiologies. Patients at higher risk of delirium (e.g., advanced age, chronic hypertension) will be included in our study. Additionally, other common risk factors that exist in this patient population (e.g., alcohol or nicotine use) are thought to contribute to delirium postoperatively. [19])

2. Competent to provide informed consent.

Exclusion criteria:

1. Emergency surgery
2. Monitored Anesthesia Care (i.e., regional anesthesia alone without plans for general anesthesia)
3. Surgery involving the eye, eyebrow, forehead, or frontal scalp near the sensor placement
4. Poor health literacy (see next section)
5. Patients with an allergy, or have experienced any drug reaction to ketamine will be excluded.
6. Pregnant or lactating patients
7. Patients in active alcohol withdrawal
8. Patients with chronic pain who are taking buprenorphine

Subject Replacement

Subjects who are not admitted to the Intensive Care Unit after surgery, will be replaced, but will be followed per protocol through the final visit 2-6 weeks post-operatively.

Recruitment Plan/Eligibility Screening:

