Patients undergoing surgical procedures requiring general anesthesia will first be approached for participation during the patient's preoperative visit, at the preoperative ENT clinic visit or on the day of surgery. A clinical research coordinator or other research personnel will be available to answer questions and obtain informed consent from the patient. It will be made clear to the patient that study participation is optional and that they can "opt out" at any time even if they have signed a consent form. In order to assure that our study participants are capable of understanding the information provided in the informed consent a single question screen will be used to detect inadequate health literacy: "How confident are you filling out medical forms by yourself?". This has been used in previous hospitals to detect poor health literacy [20]).

We intend on enrolling up to 100 male and female patients that meet eligibility criteria in order to have 60 patients who complete all study assessments. In addition to examining the potential effects of age, anesthetic drugs, and other patient and clinical factors on cognitive trajectories post-anesthesia, gender will be recorded and statistically examined as a potential contributor to different EEG patterns among our patients in this observational study.

8. Procedures:

- Upon enrollment, demographic data and medical history will be collected, subjects will be questioned about obstructive sleep apnea (OSA) using the STOP-Bang Questionnaire [21]). They will also be screened for cognitive impairment using Mini-Cog, Mini-Mental Status Examination (MMSE) and the Cognitive Failure Questionnaire (CFQ). A baseline pain assessment will be performed using the Visual Analog Scale. A baseline assessment of delirium will be obtained using the Confusion Assessment Method for Intensive Care Unit (CAM-ICU) criteria.
- Patients will be randomized to one of three groups on the morning of surgery by the Investigational Drug Service, before they enter the operating room. A randomization table will be provided and the subject assignment will be the next available number on the list. The study staff will be blinded to the list and the assignment. Group 1 will be given 0.5mg/kg of ketamine pre-incision as an intravenous (IV) bolus. Group 2 will receive 1.0mg/kg of ketamine pre-incision as

an IV bolus. Group 3. Will be administered saline/ placebo pre-incision an IV bolus. The provider will be blinded to the treatment assignment.

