This monitoring plan is appropriate, since ketamine, an anesthetic drug, has an excellent safety profile and is commonly used in anesthetic practice. In addition, the doses used in this study are unlikely to cause major or minor side effects (e.g., emergence reactions, hallucinations).

10. Statistical analysis

a. Sample size:

It was assumed about 30% delirium incidence in our population by standard care [1] [2] [3].

Estimating 5-8 oropharyngeal cancer surgeries per week with a conservative enrollment rate of 50%, we will be able to recruit 130-208 patients in 12 months. We plan to enroll about 85 eligible patients in order to achieve 20 completed patients in each randomized group. For this pilot study, with this sample size we will have 85% statistical power under significant level of 0.05 to detect delirium incidence rate drop at least 30% (placebo) to 5% (two treatment arms combined) by one-sized Mantel Haenszel test, and such effect size is supported by an existing trial [13].

b. Data analysis:

For primary aim, the incidence of delirium will be calculated in each of three randomized group with 95% confidence interval (CI), and compared between each ketamine treated group with placebo group through Fisher's exact test. For secondary aims, the dose response effect of ketamine on delirium reduction will be tested by Cochran-Armitage trend test. For other outcomes, such as pain (and/or change from baseline), MMSE (and/or change from baseline), EEG data, length of stay (LOS), and use of narcotics will be first described by summary statistics (mean, median, standard deviation, frequency, and etc.) by three randomized groups and then compared by Chi-square test/Fisher's exact test, ANOVA, or Krusal-Wallis test wherever appropriate. The analysis will be

conducted by the Biostatistics and Bioinformatics Shared Resource at Winship Cancer Institute.

The Winship OnCore system will be used for data entry and analysis.

11. Confidentiality

The privacy of the research subjects will be ensured through standard procedures for securing research data. Whenever possible, a study number, rather than a name, will be used on study records. Identifying information will not appear when we present or publish the study results. All interactions with subjects during the study will occur in a private setting. Only Emory owned computers will be utilized to store data with any identifiers and these are compliant with the Emory disc encryption policy.

12. Literature:

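### Section 10b compares EEG only across the randomised arms, so Secondary Aim 3 (EEG as a predictor of delirium) has no analysis that answers it

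*Combined protocol and SAP*

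**What the plan says.** Section 4, Secondary Aim 3, is to "Determine if raw EEG data can predict postoperative delirium during general anesthesia", with the hypothesis that the two are correlated. Section 6 lists as secondary outcome 4 "Off line EEG analysis to correlate with postoperative delirium".

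Section 10b names EEG in a single sentence on the remaining outcomes: "EEG data, length of stay (LOS), and use of narcotics will be first described by summary statistics", then "by three randomized groups and then compared by Chi-square test/Fisher's exact test, ANOVA, or Krusal-Wallis test wherever appropriate".

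Other sections describe parts of the EEG work:
- The Abstract says the device is used to "gather raw EEG data for off line analysis among patients developing post-operative delirium".
- Section 5 describes "developing a taxonomy of specific states leading up to and through emergence" and states "Our study involves quantitative EEG analysis of multiple electrodes placed over frontal brain regions".
- Section 7 adds that "gender will be recorded and statistically examined as a potential contributor to different EEG patterns".
- Section 8 and the Appendix A schedule have EEG captured in every patient, with sensors applied before induction.
- Appendix A, footnote 1, places study drug just after induction.
- The Provider Instructions (Appendix B, Table 1) ask for separate electrode taps at induction, study drug, end of surgery and emergence.

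**The concern.** Aim 3 needs patients grouped by whether they became delirious. Section 10b groups them by the treatment they were given. The phrase on appropriateness leaves open which test is used, but the grouping is fixed as the three arms.

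Followed as written, the plan would report a p-value for EEG that bears on a different question. A significant result would mainly reflect ketamine's effect on the EEG, and a null result would say little about prediction. The aim would remain unanswered although the data needed for it are collected.

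A second issue arises once the right comparison is made. EEG around emergence, which Section 5 emphasises, is recorded after study drug. If ketamine alters both EEG and delirium, an unadjusted comparison by delirium status can show an association that is absent within each arm. The plan does not say whether Aim 3 means prediction across the whole trial population or a link within arm.

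**Working it through.** **The plan's own figure.** The only power statement (Section 10a) is 85% for placebo against the two ketamine arms combined: 20 v 40 patients, 30% v 5% delirium, alpha 0.05, one-sided Mantel-Haenszel. With a events on placebo, m events in total, n1 = 20, n2 = 40 and N = 60, the statistic is (a − n1·m/N) / √[n1·n2·m(N − m) / (N²(N − 1))]. Exact binomial enumeration gives 84.8%, so the figure reproduces. It concerns ketamine and delirium and gives no information on Aim 3.

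**Inputs for the EEG question.** From Section 10a: 20 completers per arm, and 30% and 5% delirium. Assumed, because the documents do not give them: complete EEG and CAM-ICU data in all 60 patients, a normally distributed EEG feature with SD 1, the EEG effect sizes, and alternative ketamine-arm delirium rates of 15% and 30%.

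**Expected delirium cases.**
- 30/5/5%: 20×0.30 + 40×0.05 = 8
- 30/15/15%: 6 + 6 = 12
- 30/30/30%: 6 + 12 = 18

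**Why the by-arm test misses a real link.** If delirious patients differ by 1 SD on the EEG feature and ketamine does not affect EEG, the arm means differ only through the mix of cases: 0.30 − 0.05 = 0.25 SD at 30/5/5%, 0.15 SD at 30/15/15%, and 0 at 30/30/30%.

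**Why the unadjusted by-status test can mislead.** Suppose ketamine shifts EEG by 1 SD and EEG has no within-arm link to delirium. At 30/5/5%, the share treated with ketamine is 2/8 = 25% among cases and 38/52 = 73% among non-cases, a spurious difference of about 0.48 SD. At 30/15/15% it is 34/48 − 6/12 = 0.71 − 0.50 = 0.21 SD. At 30/30/30% it is 28/42 − 12/18 = 0.

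**Simulation** (two-sided 0.05, 10,000 runs per cell; percentage of trials significant, approximate; adjustment by a linear model with arm):

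| Scenario | Test | 30/5/5% | 30/15/15% | 30/30/30% |
|---|---|---|---|---|
| True 1-SD difference by delirium status | By-arm ANOVA | 11 | 7 | 5 |
| | By status, unadjusted | 71 | 84 | 93 |
| | By status, adjusted for arm | 64 | 82 | 92 |
| Drug-only 1-SD shift | By-arm ANOVA | 90 | 90 | 90 |
| | By status, unadjusted | 21 | 9 | 5 |
| | By status, adjusted for arm | 5 | 5 | 5 |

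Firth logistic regression with arm gives 62%, 80% and 91% for the true difference, and stays at about 4 to 5% for the drug-only shift.

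**Precision.** A 1-SD difference corresponds to AUC = Φ(1/√2) = 0.76. The Hanley-McNeil variance is [A(1 − A) + (n1 − 1)(A/(2 − A) − A²) + (n0 − 1)(2A²/(1 + A) − A²)] / (n1·n0), where n1 and n0 are now cases and non-cases. With 8 v 52 this is about 4.45/416, so the 95% half-width is about 0.20. With 18 v 42 it is about 4.01/756, half-width about 0.14.

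**Limits of an arm-stratified AUC at 30/5/5%.** Each ketamine arm expects 20×0.05 = 1 case. The chance that a given ketamine arm has none is 0.95^20 = 36%. The chance that at least one of the two has none is 1 − (1 − 0.358)² = 59%. Expected within-arm case-control pairs are 20×19×0.30×0.70 = 79.8 on placebo and 20×19×0.05×0.95 = 18.05 on each ketamine arm, so about 70% come from placebo (79.8/115.9 = 69%; about 71% as the simulated mean share).

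**The case against.** The other side has good points. This is a pilot, EEG is presented throughout as a possible predictor, and the sentence in Section 10b is a catch-all that nowhere claims to be the test of Aim 3. The intention to relate EEG to delirium is stated several times. All of that stands and limits the weight of the point. It does not supply the missing analysis: Section 10b gives the primary aim and the dose-response aim each a named test, while the only comparison given for EEG addresses a different question.

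Several stronger readings are tempting and are not supported:
- A reader might infer that Section 10b contradicts Sections 4 and 6. It does not, because a by-arm EEG summary and an EEG-delirium analysis can both be done.
- A reader might infer from the Abstract that only delirious patients' EEG will be analysed, which would leave no comparison group. EEG is captured in everyone, so this is more likely loose wording and is a side point.
- A reader might infer that there is no EEG plan at all. Acquisition, frontal quantitative analysis, an emergence focus, time markers and a gender comparison are all described.
- A reader might infer that features will be chosen after the results are seen. The documents do not say when they will be fixed.
- A reader might infer that an unadjusted analysis is wrong. Marginal prediction is a legitimate reading of the aim, and an association that runs through treatment is still prediction in that sense.

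The confounding figures also rest on an assumption: no passage says that a single bolus after induction shifts the EEG at emergence, or by how much.

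**Conclusion.** The point holds as an unanswered secondary aim and should be fixed. The plan's only EEG comparison cannot show whether EEG is related to delirium, and nothing elsewhere fills the gap.

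The text alone establishes this. The simulated percentages show only how far the two questions can diverge, and they depend on the assumed EEG effects and complete data. The case for arm adjustment is conditional: under a drug-only 1-SD shift, false positives in the unadjusted comparison are about 21% at the plan's own rates, about 9% at 30/15/15%, and nominal if ketamine does not change delirium. It applies only to EEG recorded after study drug. The primary analysis is not touched.

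**What to change.** Add to Section 10b:

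> Aim 3 (exploratory): in all randomised patients with usable EEG and post-operative CAM-ICU data, one or two EEG features from a stated epoch, fixed before unblinding, will be compared between patients with and without delirium (primary-outcome definition). For an epoch after study drug, the association will be adjusted for arm by a small-sample method (for example Firth logistic regression). An unadjusted AUC with 95% CI may be reported as marginal prediction, labelled as possibly reflecting the drug's effect on EEG.

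An epoch before study drug needs no arm adjustment for this reason. One can be identified, since sensors go on before induction and induction and study drug are marked separately. Keep the by-arm EEG summary as descriptive. Reword the Abstract so that EEG from patients with and without delirium is analysed.

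The cost is wording and one modest analysis, with no new data collection. The downsides should be stated in the plan:
- About 8 cases are expected at the plan's rates (18 if ketamine has no effect), so the AUC is known only to within about ±0.20 (±0.14).
- Adjustment costs some power: about 71% falls to 64% in the illustration.
- The analysis set may shrink, because Appendix A, footnote 4, has ward-phase CAM-ICU scores only for the ICU stay and as available.
- An arm-stratified AUC should be optional, since at 30/5/5% it would be mainly a placebo-arm estimate and often undefined in a ketamine arm.

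### Secondary Aim 2 expects a larger fall in pain at the higher dose, but section 10b compares pain across arms with an omnibus test that ignores dose order and tests no direction

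*Combined protocol and SAP*

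**What the plan says.** Section 4 (Objectives), Secondary Aim 2, has two parts. The aim is to "Determine if a single dose of ketamine will reduce post-operative pain and opioid requirements". The hypothesis attached to it is narrower and ordered by dose: "Our hypothesis is that the higher dose of ketamine will lead to a more profound decrease in objective pain scores". That ordering is written for pain scores; none is written for opioid use.

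Section 10b (Data analysis) gives delirium an ordered test: "the dose response effect of ketamine on delirium reduction will be tested by Cochran-Armitage trend test". Pain and narcotic use fall in a general list: "For other outcomes, such as pain (and/or change from baseline), MMSE (and/or change from baseline), EEG data, length of stay (LOS), and use of narcotics". These "will be first described by summary statistics" for each arm and are then compared by a chi-square or Fisher test, "ANOVA, or Krusal-Wallis test wherever appropriate". For pain and narcotic use, 10b names no trend test, contrast, pairwise comparison, confidence interval or direction.

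Section 10a sets the size: enrolment is planned "in order to achieve 20 completed patients in each randomized group", so three arms and 60 completers.

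**The concern.** ANOVA and Kruskal-Wallis treat the three arms as unordered labels. A significant result says only that the arms are not all alike. It does not say that ketamine lowers pain, or that 1.0 mg/kg lowers it more than 0.5 mg/kg. It would be just as significant if 0.5 mg/kg were the only arm to differ, which is a pattern that contradicts the hypothesis.

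For delirium, the plan pairs a dose-response hypothesis with an ordered test. For pain, a parallel hypothesis gets no ordered test, and no reason is given. At stake are the interpretability of the pain and opioid results and, under some dose-response shapes, some power.

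**Working it through.** **The plan's own figure.** No power, effect size or SD is stated for pain or opioids. The only stated power, 85% in section 10a, is for delirium (30% on placebo, n = 20, against 5% on the two ketamine arms combined, n = 40, one-sided 0.05, Mantel-Haenszel). Exact enumeration of that test without continuity correction gives 84.8%, so the figure reproduces. It says nothing about pain.

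**Inputs.** From section 10a: n = 20 completers per arm. Assumed: two-sided 0.05; one normally distributed pain value per patient with equal SD; total effect d (1.0 mg/kg against placebo, in SD units) from 0.4 to 1.0; several dose-response shapes.

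**Formulas.**
- Omnibus ANOVA: noncentral F on (2, 57) df with λ = 20 × Σ(μᵢ − mean)² / SD².
- Linear contrast: dose scores 0, 0.5, 1.0 centre to weights proportional to (−1, 0, 1). Noncentral t on 57 df with δ = d / √(2/20).

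**Worked case, linear, d = 0.8.** Means 0, 0.4, 0.8 deviate from their average by −0.4, 0, 0.4. So λ = 20 × 0.32 = 6.4, and δ = 0.8 / 0.3162 = 2.53, with δ² = 6.4. The noncentrality is the same, but the omnibus test spreads it over 2 df: 58.9% against 70.1%.

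**Linear response.**

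| d (SD) | Omnibus F | Linear contrast | Gain (points) |
|---|---|---|---|
| 0.4 | 18.0% | 23.8% | 6 |
| 0.5 | 26.1% | 34.3% | 8 |
| 0.6 | 36.1% | 46.2% | 10 |
| 0.7 | 47.3% | 58.6% | 11 |
| 0.8 | 58.9% | 70.1% | 11 |
| 0.9 | 69.9% | 79.9% | 10 |
| 1.0 | 79.3% | 87.5% | 8 |

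The rank tests behave alike. By simulation on normal data (8,000 runs) at d = 0.8, Kruskal-Wallis has 55% and Jonckheere-Terpstra 68%.

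**Other shapes.** The contrast's power depends only on d, because the 0.5 mg/kg mean has weight zero. The omnibus power changes with shape.
- Low dose gives 75% of the effect: at d = 0.8, 62.6% against 70.1%, a gain of 7.5 points. Across 0.5 to 1.0 SD the gain is 5 to 7.5 points.
- Plateau (both doses equal): at d = 0.8 the deviations are −0.533, 0.267, 0.267, so λ = 20 × 0.427 = 8.53. The omnibus test has 72.3% and the contrast 70.1%, a loss of 2 points. The loss is 2 to 3 points over 0.8 to 1.0 SD; at 0.5 SD the tests are level (33.7% against 34.3%).
- Only 0.5 mg/kg differs, by 0.8 SD: again λ = 8.53, so the omnibus test has 72%. The contrast has δ = 0, so it rejects at its 5% level.

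**1.0 minus 0.5 mg/kg.** In the linear 0.8 SD case this difference is 0.4 SD. With δ = 0.4 / 0.3162 = 1.26 on 57 df, power is about 24%.

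**The case against.** The best defence is that this is a pilot with an unknown dose-response shape, where an omnibus test is a reasonable choice because it assumes no shape. That has force: if only 0.5 mg/kg works, the omnibus test finds it and the contrast does not. It is a reason to keep the omnibus test as support, but it does not make that test an answer to Aim 2.

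Four stronger readings are tempting, and the documents do not support them.

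- A reader might infer that the plan loses about 10 points of power. That needs a roughly linear response and about 0.6 to 0.9 SD, and the documents give neither. The gain is smaller for other shapes and reverses under a plateau. The calculation also uses one value per patient, while sections 6 and 8 describe repeated scores on observer and patient scales, and 10b does not define a summary.
- A reader might infer that opioid use is also predicted to fall more at the higher dose. Aim 2 states only a reduction for opioids.
- A reader might infer that the direction of effect would be unknown. Section 10b reports summaries by arm, so direction would be visible, though not tested. Leaving the choice among the listed tests to what is appropriate does not pre-specify an ordered one.
- A reader might infer that a significant trend test would prove that 1.0 mg/kg beats 0.5 mg/kg. With weights (−1, 0, 1) it compares 1.0 mg/kg with placebo; under a plateau at 0.8 SD it rejects 70% of the time although the doses are equal.

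**Conclusion.** The mismatch stands. Aim 2 is directional for pain and opioid use and dose-ordered for pain, while the planned inference for both is unordered and non-directional, so it cannot answer the aim as written.

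The power consequence is conditional on the assumptions shown above: a gain of about 6 to 11 points for an ordered contrast if the response is linear, 5 to 7.5 if the low dose gives three quarters of the effect, and a loss of 2 to 3 under a plateau at the larger effects. The case for change rests mainly on matching the analysis to the hypothesis and on having estimates with intervals; the possible power gain is secondary. Since this is one secondary aim of a pilot and the primary analysis is untouched, it is a cheap improvement of lower priority.

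**What to change.** Amend section 10b before unblinding:

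1. For pain, name a linear dose contrast (scores 0, 0.5, 1.0) as the Aim 2 test, or Jonckheere-Terpstra if the data are skewed, in line with the trend test already planned for delirium.
2. For pain and narcotic use, report each dose minus placebo and 1.0 minus 0.5 mg/kg with 95% CIs. Say that the question of whether the higher dose does more rests on the last of these, read as an estimate given its low power.
3. Keep ANOVA or Kruskal-Wallis as a supporting analysis, so that a non-monotone response is not overlooked.
4. State whether opioid use is also expected to be dose-ordered. If so, apply the ordered test there too.

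The cost is a few sentences, with no extra patients, data or procedures. The statistical price is 2 to 3 points of power under a plateau at larger effects, and near-blindness of the contrast to a response confined to 0.5 mg/kg, which items 2 and 3 are there to cover.
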